## 12.0 Participant Information

**12.1 Subject Population:**

Patients considered for this study will include adults aged 18 to 55 years who present to the ED for management of acute musculoskeletal pain with an intensity of 20 or greater on a standard 100mm visual analog scale and who would routinely be treated with intramuscular ketorolac in the WBAMC ED as determined by the attending emergency room medical provider. Subjects must also not be pregnant or lactating to be eligible for enrollment.

**12.2 Age Range:**

Check all the boxes that apply. If the age range of potential subjects (specimens, records) does not match the range(s) selected, please specify in the text box.

- 0-17
- 18-24
- 25-34
- 35-44
- 45-54
- 55-64
- 65-74
- 75+

18 - 55

**12.3 Gender:**

Male  
 Female  
 Other

#### 12.4 Special categories, check all that apply

Minors /Children  
 Students  
 Employees - Civilian  
 Employees - Contractor  
 Resident/trainee  
 Cadets /Midshipmen  
 Active Duty Military Personnel  
 Wounded Warriors  
 Economically Disadvantaged Persons  
 Educationally Disadvantaged Persons  
 Physically Challenged (Physical challenges include visual and/or auditory impairment)  
 Persons with Impaired Decisional Capacity  
 Prisoners  
 Pregnant Women, Fetuses, and Neonates  
 Non-English Speakers  
 International Research involving Foreign Nationals - Headquarters Review is necessary

#### 12.5 Inclusion Criteria:

Order Number	Criteria
1	
Age 18-55 years of age
 
Study subject is one of the following; DoD service member, DoD beneficiary, or Veteran Affairs beneficiary
 
ESI 4 or 5
 
Presenting to WBAMC ED for management of musculoskeletal pain (i.e., general muscular, neck, back, shoulder, arm, forearm, elbow, wrist, finger, hip, knee, thigh, leg, ankle, foot or digits)
 
Pain intensity of 20 mm or greater on a standard 100 mm visual analog scale
 
Pain duration less than 30 days
 
Attending provider concurs with intramuscular ketorolac administration for analgesia

#### 12.6 Exclusion Criteria:

Order Number	Criteria
	
Patients weighing less than 50 kg (110 lbs)
 
Patients younger than 18 or older than 55 years
 
Pregnant or breast feeding

	History of: confirmed, unconfirmed, known, unknown, or suspected peptic ulcer disease, intestinal hemorrhage, renal insufficiency, hepatic insufficiency, cerebrovascular bleeding, hemorrhagic diathesis, incomplete hemostasis, dark stools, bright red blood per rectum, hemoptysis, easy bruising, or high risk of bleeding
	Unable to confidently convey or unknown medical history
	Allergy or hypersensitivity to nonsteroidal anti-inflammatory drugs or Aspirin
1	Systolic blood pressure <90 or >180 mmHg; pulse rate <50 or >150 beats/min
	Any over-the-counter or prescribed opioid and/or non-opioid analgesic medication (oral, per rectum, topical or parenteral) taken within 12 hours of ED presentation
	Advised by any medical provider to not receive non-steroidal anti-inflammatory drugs (NSAIDs) for any reason
	Pain duration greater than 30 days
	Refusal to remain in the WBAMC ED for up to 60 minutes after injection of ketorolac
	Patients currently taking anticoagulant medications
	Concurrent use of medications which are contraindicated with concomitant NSAID use. These drugs include aspirin, probenecid and pentoxyfylline

## 13.0

### Recruitment and Consent

#### 13.1 Please describe the recruitment process, including how subjects will be identified and selected for the study.

Potential subjects will be verbally recruited for participation in the study utilizing a preformatted verbal synopsis. In a private setting (ED room or ED bay) at the WBAMC ED [name], potential subjects will be notified of their initial eligibility and provided with a verbal synopsis of the study to include objectives, benefits, and risks. This is not a formal consent process but will provide potential subjects with a basic overview of the study and obtain their verbal willingness to pursue participation further. Potential subjects at this point may agree with participation in the study, decline participation or request time to consider participation. Potential subjects who decline participation will be thanked for their time and escorted back to the WBAMC ED waiting room. Potential subjects who request time to consider participation will be given until they are roomed within the WBAMC to make a decision. This time frame is dependent on WBAMC ED wait times and may be minutes or may be hours. Should a potential subject decide to participate after consideration, their request will be honored: as long as they have not been roomed or their participation would interfere with the study process or randomization at that time. No PHI or PII will be documented on these potential subjects.

#### 13.2 Compensation for Participation:

Patients will not be compensated for participation in this study.

**13.3 Please describe the pre-screening process. If no pre-screening, enter Not Applicable in the text editor**

The investigators will monitor the WBAMC ED electronic health record (EHR) T-System™ (manufactured by T-System™ Incorporated) for all patients presenting to the WBAMC ED with an Emergency Severity Index (ESI) score of 4 or 5 meeting inclusion criteria age and having a chief complaint of musculoskeletal (MSK) pain. T-System™ is the ED EHR used to electronically document all aspects of patient medical care from ED registration through discharge. However, individual patient ED medical records will not be accessed for the purposes of this research. Only the T-System™ “Home” screen will be accessed and viewed when prescreening patients for this study, and the remainder of this study will not require access to any other part of the patient ED EHR. The T-System™ home screen does not provide detailed patient medical information, such as a patient history, treatment or diagnosis. It does provide the viewer with the following:

1. Area (the general area or section of the WBAMC ED where the patient is physically located-this could be either in the “main ED” or in the “fast track section”)
2. Room (the actual ED room number where the patient is located)
3. Patient name
4. Chief complaint
5. Triage category (ESI category)
6. Nurse(s) name(s) assigned to the patient
7. Physician(s) or provider(s) name(s) assigned to the patient
8. Comments
9. Disposition of the patient (admit, discharge, etc.)

There are other categories on the screen for vital signs and orders, but these do not display specific vital signs or specific orders, unless accessed by the user through “clicking” on these categories. The vital signs category will be accessed to determine if the patient’s heart rate, temperature and blood pressure meet inclusion criteria. However, for the purposes of this study-no other protected health information (PHI) or personally identifiable information (PII) will be accessed, viewed or used. Again, the T-System™ home screen will be used only to determine the age of the potential subject, their ESI category and their chief complaint (and vital signs, but this is during the screening process). This data will be used to prescreen and identify any potential subjects for this study and to initiate the recruitment process. The data identified during this process is not recorded anywhere. Patients meeting the three above prescreening criteria will be considered potential subjects.

When prescreening T-System™ for a chief complaint of MSK pain, it should be known that MSK pain is a blanket term which encompasses many different types of injuries and/or pain. For completeness, a definition of MSK pain, as pertinent to this study, is located in the definitions section of this document. However, for brevity, the term MSK pain will be utilized throughout the remainder of this document.

The ESI is a standardized ED triage algorithm utilized nationwide to stratify patient triage acuity. ESI scores range from 1 to 5, with 1 being the most emergent medical conditions and 5 being the least emergent medical conditions. For an example, a patient with an ESI score of 1 may have severe trauma or present in cardiac arrest, whereas a patient with an ESI score of 5 may only require a medication refill or suture removal. For the purpose of this study, only ESI scores of 4 or 5 will be included. The rationale for excluding ESI categories 1-3 is that ESI categories of 4 and 5 are unlikely to have been the result of, or develop into a serious injury or illness during a patient’s ED stay. ESI categories 1-3 may require extensive laboratory, imaging and/or opiate pharmacotherapy during their ED stay, which may confound study results. Whereas, a patient presenting with an acute MSK injury or pain and an ESI category of 4 or 5 will have a greater likelihood of being treated with a single non-opioid analgesic, such as ketorolac. Therefore, by choosing ESI categories 4 or 5, our study makes it unlikely that the patient has a serious medical process (or that a serious medical issue will develop during their ED stay) and/or will require opiate analgesics during their ED stay. Also, selecting for ESI categories 4 or 5 increases the likelihood of ketorolac being the only analgesic required during their ED stay. A complete explanation of ESI scores is beyond the scope of this document; more information can be obtained at <https://www.ahrq.gov>. Subjects who meet the age inclusion criteria, have an ESI score of 4 or 5 and a chief complaint of MSK pain will be considered prescreened as potential subjects for enrollment in this study.

Note: the primary investigator will be conducting the research during time allocated for research. He will not be a part of the care team for the potential study subjects.

#### **13.4 Consent Process:**

**Revised Common Rule, Section 219.116: General requirements for informed consent, whether written or oral, are set forth in this paragraph and apply to consent obtained in accordance with the requirements set forth in paragraphs (b) through (d) of this section. Broad consent may be obtained in lieu of informed consent obtained in accordance with paragraphs (b) and (c) of this section only with respect to the storage, maintenance, and secondary research uses of identifiable private information and identifiable biospecimens.**

Are you requesting a waiver or alteration of informed consent?

Yes  No

Please explain the consent process:

Potential subjects will then be verbally recruited for participation in the study. In a private setting (ED room or ED bay), potential subjects will be notified of their initial eligibility and provided with a verbal synopsis of the study. The verbal recruited will be performed by the investigator reading the scripted verbal synopsis document, which is attached as an appendix to this protocol submission. This will provide potential subjects with a basic overview of the study and obtain their verbal willingness to pursue participation further. Potential subjects at this point may agree with participation in the study, decline participation or request time to consider participation. Potential subjects who decline participation will be thanked for their time and escorted back to the WBAMC ED waiting room.

Potential subjects who request time to consider participation will be given until they are roomed within the WBAMC to make a decision. This time frame is dependent on WBAMC ED wait times and may be minutes or may be hours. Should a potential subject decide to participate after consideration, their request will be honored: as long as they have not been roomed. No PHI or PII will be documented on these potential subjects.

Potential subjects who grant verbal willingness to participate in this study will then be formally consented. The consent process includes a complete description of the study to include objectives of the study, benefits to the DoD, process, subject time commitment, risks, benefits, alternatives and documentation to be completed by subject. Only after the consent process is described, all of the inclusion criteria are met and none of the exclusion criteria are met, will potential subjects be fully screened. This includes females being screened for pregnancy using a point-of-care (POC) urine human chorionic gonadotropin (UHCG) test (urine pregnancy test). Additionally, to complete enrollment in to the study, subjects will be asked to sign the HIPAA Authorization Form. The HIPAA Authorization Form authorizes investigators access to protected health information (PHI) and Personally Identifiable Information (PII) for purposes only pertaining to this study.

Named investigators on this protocol will conduct the consent process for all subjects enrolled in this study.

Potential subjects who grant verbal willingness and permission to participate in this study will then be consented. The consent process includes a complete description of the study to include objectives of the study, benefits to the DoD, process, subject time commitment, risks, benefits, alternatives and documentation. Only after the formal consent process is described, all of the inclusion criteria are met and none of the exclusion criteria are met, will potential subjects be officially consented using the Informed Consent Form attached with this protocol submission.

Female potential subjects will be consented for a point-of-care (POC) urine human chorionic gonadotropin (UHCG) test (urine pregnancy test).

Upon meeting all of the aforementioned criteria for enrollment, providing a signature on the Informed Consent Form and HIPAA Authorization Form, the potential subject will be considered enrolled as a subject for the study.

#### **13.5**

**DoDI 3216.02 requires an ombudsman to be present during recruitment briefings when research involves greater than minimal risk and recruitment of Service members occurs in a group setting. If applicable, you may nominate an individual to serve as the ombudsman.**

N/A  
 Propose ombudsman

### **13.6 Withdrawal from Study Participation:**

Explain the process for withdrawal and specify whether or not the subjects will be given the opportunity to withdraw their data their data/specimens in the event they wish to withdraw from the study

Withdrawal from participation in this study will not cause any undue harm or additional risk to the subject. If the subject wishes to withdraw from the study, they need only to verbally declare their withdrawal from participation. The subject will be informed that their rights for medical treatment will not be impacted in the case of study withdrawal. The patient may be allowed to withdraw at any point throughout the study period and all PHI, PII and data collected at that time will be destroyed in accordance with WBAMC sensitive document disposal policies. Withdrawal or exclusion will be documented on a separate document for record purposes and no PHI or PII will be retained.

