    1. Objective adverse events are those identified during reassessment immediately following the initial ketorolac administration, and at the 30 minute and 60 minute re-evaluation intervals. To better facilitate analysis, a list of the most commonly occurring objective adverse events, according to UpToDate.com, will be provided for the investigator to choose from. This list will be included on the Ketorolac Research Form. Objective adverse events are any (1.) subjective events (signs or symptoms) which can be validated or observed by study investigators (such as diaphoresis), (2.) are obvious to the investigator, but perhaps not the patient (mild facial swelling or rash) or (3.) abnormal vital signs. Blood pressure and heart rate measurements will be taken at the 30 minute and 60 minute intervals. Any deviation of blood pressure or heart rate which would meet exclusion criteria for this study would prompt immediate notification of the attending provider and the patient would be excluded from the study.
    2. Subjective adverse events are any symptoms conveyed by the subject, but are not measureable, observable or verifiable by the investigator. To better facilitate analysis, a list of the most commonly occurring subjective adverse events, according to UpToDate.com, will be provided to the study subject to choose from. Examples of subjective adverse events may include dizziness, light headedness or nausea (this is not an exhaustive list of subjective adverse events).
2. Informed Consent Form: this document describes important details and purpose of the research, risks, benefits, alternatives, use of PHI and PII, obtains consent from female potential subjects for a POC UHCG and obtains official consent in the form of the subject's signature. This form will be explained in detail with the patient to ensure their complete and total understanding. The patient will be given as much time as possible to contemplate the decision to enroll as a subject in this study. However, once roomed in the ED, the patient will no longer be eligible to enroll. The patient will be given the opportunity to ask as many questions as possible prior to obtaining signature and will be informed that they have the right to withdraw from the study at any point.

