#### Secondary Outcome Variable Data.

The secondary outcome variables will be the number of subjects experiencing adverse events (both objective and subjective). This data will be provided by the subjects or observed, measured or verified by the investigators and will be documented on the adverse events section of the Ketorolac Research Form. Adverse events will be documented as objective and subjective adverse events. Subjects will be provided a list of the most common adverse events based on the medical website UpToDate.com. This list will be included on the Ketorolac Research Form. Subjects will be advised to circle any of the adverse events that they are experiencing. Each circled adverse event will count as 1 in a binary numbering system (1 indicating an adverse event and 0 indicating no adverse event) for purposes of analysis. Subjects may have more than one adverse event and each event will count as 1 point. The definitions of objective and subjective adverse event are provided below.

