##### 1. Objective adverse events

1. Objective adverse events will be described based on objective findings found during reassessment immediately following the initial ketorolac administration, and at the 30 minute and 60 minute re-evaluation intervals. Objective adverse events are any (1.) subjective events (signs or symptoms) which can be validated or observed by study investigators (such as rash or obvious dyspnea), (2.) are obvious to the investigator, but perhaps not the patient (mild facial swelling or rash) or (3.) abnormal vital signs. Blood pressure and heart rate measurements will be taken at the 30 minute and 60 minute intervals. Any deviation of blood pressure or heart rate which would meet exclusion criteria for this study would prompt immediate notification of the attending provider and the patient would be excluded from the study.

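### Data already collected are destroyed on withdrawal, and dosed subjects with out-of-limit vital signs are excluded, so some adverse events can leave the arm comparison and withdrawn subjects' pain data cannot be recovered

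*Protocol*

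**What the plan says.** **Withdrawal.** Protocol section 13.6: "The patient may be allowed to withdraw at any point throughout the study period", which includes the time after dosing, and "all PHI, PII and data collected at that time will be destroyed". What remains is a bare record: "Withdrawal or exclusion will be documented on a separate document for record purposes and no PHI or PII will be retained". The template prompt in that section asks whether subjects may choose to withdraw their data. The answer states no choice.

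**Vital signs after dosing.** Section 10.2, Objective adverse events, lists "3.) abnormal vital signs" as the third kind of objective adverse event. The same paragraph covers the 30- and 60-minute readings. A deviation that meets the exclusion criteria "would prompt immediate notification of the attending provider and the patient would be excluded from the study". Section 10.1 repeats the rule in its description of the Ketorolac Research Form ("Any deviation of blood pressure or heart rate which would meet exclusion criteria for this study"). The limits are in section 12.6: "Systolic blood pressure <90 or >180 mmHg; pulse rate <50 or >150 beats/min".

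**Endpoint.** Section 10.2: "The secondary outcome variables will be the number of subjects experiencing adverse events (both objective and subjective").

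**Analysis.** Section 11.1 prompts for the handling of missing data, but the answer gives none. Section 11.6 and the SAP name the tests (t-test for pain; a z-test in the protocol and Fisher's exact test in the SAP for adverse events). Neither document defines an all-randomised set or a safety set.

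**The concern.** Two rules act on subjects who have already been dosed. The first erases what was recorded before withdrawal. The second removes a subject because of an event that the secondary outcome is meant to count. With no analysis set to restore them, a reader following the protocol would leave both groups out of the comparison.

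Losses of this kind need not be neutral. Section 14.1 says that risks rise with dose and that subjects on 15 mg may have inadequate pain control. Section 11.1 expects the higher dose to do better on average. Withdrawal for poor relief could therefore fall more on 15 mg, which would favour non-inferiority. Loss for harm could fall more on 60 mg, which would mask the adverse-event difference that section 11.6 sets out to test. Destroyed data cannot be brought back for a sensitivity analysis.

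**Working it through.** **1. The plan's own figure.** Section 11.5: margin 13 mm, SD 27 mm, true difference 0, one-sided alpha 0.05.
- Standard error at 55 per arm: 27 × √(2/55) = 5.15 mm.
- Power by noncentral t: 0.7998 at 54 and 0.8063 at 55 per arm, so the stated 55 reproduces.
- Dropout allowance: 55 × 1.1 = 60.5, taken as 61. These 6 extra subjects per arm protect power. They do not protect against losses related to outcome.

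**2. The text on adverse events.** A post-dose systolic pressure above 180 mmHg, for example, is an objective adverse event by definition and also a ground for exclusion. The protocol does not say whether the event still counts. A milder deviation is recorded and the subject stays.

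**3. Adverse-event illustration.** The documents give no expected rates by arm. Assume 9/61 on 15 mg and 18/61 on 60 mg, and remove affected subjects. Fisher's exact test is taken as one-sided, as the protocol's test is; the SAP does not state the side.

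| Affected subjects removed (15 mg, 60 mg) | 15 mg | 60 mg | One-sided p |
|---|---|---|---|
| 0, 0 | 9/61 | 18/61 | 0.040 |
| 0, 3 | 9/61 | 15/58 | 0.10 |
| 0, 6 | 9/61 | 12/55 | 0.23 |
| 3, 3 | 6/58 | 15/58 | 0.026 |

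A few removals can change the conclusion, in either direction.

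**4. Pain illustration, closed form.** Suppose k subjects per arm leave, with mean pain reduction lower than the completers' by a gap g. Completers then overstate the difference by g × (k15 − k60)/61. The true difference is set at the −13 mm margin, where the false non-inferiority rate should be 5%. The rate is a noncentral t calculation with standard error 5.15 mm.

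| k15, k60 (assumed) | g (assumed) | Bias | False non-inferiority |
|---|---|---|---|
| 6, 2 | 20 mm | 20 × 4/61 = 1.31 mm | 8.2% |
| 6, 2 | 30 mm | 30 × 4/61 = 1.97 mm | 10.3% |
| 9, 3 | 30 mm | 30 × 6/61 = 2.95 mm | 14.1% |

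**5. Pain illustration, simulation.** 20,000 trials, 61 per arm, SD 27, true difference at the margin.
- Loss unrelated to outcome: no bias, about 5%.
- Worst responders removed, 6 versus 6: no bias, about 7%.
- Worst responders removed, 6 versus 3: +2.3 mm, 15%.
- Worst responders removed, 6 versus 0: +5.0 mm, 29% (an extreme case).
- Loss only moderately related to outcome (correlation 0.5): 6 versus 3 gives +1.1 mm and 8.5%; 6 versus 0 gives +2.6 mm and 13%.

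By symmetry, heavier loss of poor responders from 60 mg would bias against non-inferiority.

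**6. Which rule produces such losses.** Sections 10.1 (Prescreening / Recruitment Process and Medication Administration) unenrol a subject who is given additional analgesia. That is the plan's main exit for poor relief. Destruction is not stated for these subjects: 10.1 stops further collection, and 10.2 (Descriptive Statistics Data) keeps data on them for description only. The figures in steps 4 and 5 therefore describe all outcome-related losses together, not section 13.6 alone.

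**The case against.** The strongest reply is that few subjects will leave under 13.6. Follow-up lasts 60 minutes, patients unwilling to stay are excluded beforehand (12.6), and a subject in pain can receive more analgesia without withdrawing. This stands. It is why the pain figures cannot be charged to 13.6.

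A reader might also infer that the worst outcomes vanish from both comparisons, or that harms are hidden. The documents do not support that:
- Destruction is stated only for withdrawal. For the vital-sign rule the text speaks of exclusion and is silent on the data already recorded.
- Only readings beyond the 12.6 limits trigger exclusion. Milder deviations, and all other adverse events in subjects who stay, are still counted.
- Section 16.1 sends serious and unexpected events to the IRB and enters expected ones in a log. That log is not named as a source for the arm comparison, so loss from the comparison remains possible.
- Section 13.6 keeps a record of each withdrawal or exclusion, though it does not specify arm, time or reason.

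A reader might further infer that the bias must favour non-inferiority. That requires poor responders to leave 15 mg more often, which is plausible but not given. Finally, the consent form is not among the documents, so it may offer a choice that the protocol does not state.

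What survives is the wording of the two rules, the absence of any analysis set or missing-data rule, and the irreversibility of destruction.

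**Conclusion.** The point holds in a limited form. Under the stated rules, some adverse events can drop out of the between-arm comparison, and pain data from withdrawn subjects cannot be recovered for any sensitivity analysis. The vital-sign wording is an unresolved conflict between an event definition and an exclusion rule, not a written instruction to delete events.

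The size is not determined by the documents, because they give no losses by arm. The 1.3 to 3.0 mm bias and 8-14% false non-inferiority rate rest on assumed losses of 6 versus 2 or 9 versus 3 and an assumed gap of 20 to 30 mm. They cover all outcome-related exits, mainly unenrolment for additional analgesia. The adverse-event counts are likewise assumed. The change is worth making because the loss is permanent and the remedy is cheap. It does not affect the stated sample size.

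**What to change.** 1. **Section 13.6.** State that withdrawal stops further collection. De-identified VAS and adverse-event data recorded up to that point are kept and analysed by randomised arm, unless the subject asks for their destruction. Align the consent form.
2. **Adverse events.** State in 10.2, 11.6 and the SAP that every dosed subject, including those with vital-sign deviations, stays in the numerator and denominator. Reconcile this with the exclusion wording in 10.1 and 10.2. This concerns data handling only; clinical management of the subject is not at issue.
3. **Reporting.** Give number, time and reason of withdrawals and exclusions by arm.
4. **Pain outcome.** Add a sensitivity analysis covering all dosed subjects, with a stated rule for missing 30- and 60-minute VAS. Retention alone does not remove the bias, since later scores stay missing and a plain t-test would still drop those subjects. Reconcile 10.1 and 10.2 on which data are kept after unenrolment for additional analgesia, so that this analysis can include those subjects.

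Cost: a short amendment, a matching consent sentence if the form needs one, and a paragraph in the SAP. No new procedures or visits are needed.
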